5 DEFINITIONS

The following definitions apply to the summary tables and statistical analyses planned for the study report:

Intent-to-treat (ITT) population: all subjects randomized to one of the treatment groups, classified according to the randomization assignment.

Safety population: all subjects who have received at least one dose of study injection and for whom any data on safety are available. Subjects will be classified according to the treatment received. The primary safety analysis will be done on this population.

Per-protocol (PP) population: all eligible subjects randomized to one of the treatment groups and who received both assigned study injections. Subjects will be classified according to the treatment received. Analysis of immunogenicity endpoints occurring after the second study injection will be performed on this population.

Immunogenicity population: all eligible subjects who have received at least one study injection, for whom data concerning post-baseline immunogenicity endpoint measures are available, and major protocol deviations are absent. The post-baseline immunogenicity endpoints may include humoral or cellular responses measured at the protocol-specified time points, or at the time of early termination.

Subjects will be classified according to the treatment received. Immunogenicity analysis will be done using this population or the Per Protocol Population, as appropriate

Baseline value: Most recent value recorded prior to the first study injection.

Treatment group: One of the two treatment assignments.

Visit Day: The scheduled Visit Day, for example Day 84.

Study Day: The day on study that a visit actually took place (date of visit minus date of enrollment, Day 0). For example, an adverse event onset might be on study day 5; or a scheduled Visit Day 84 evaluation could take place on study day 89.

Immunology laboratory assays/data/results: IgG antibody and cytokine assays/data/results.

6 DATA MANAGEMENT CONSIDERATIONS

Individual subject data will be collected on electronic case report forms (eCRFs) and stored in a proprietary database maintained by DF/Net. All reported adverse events will be coded to standard preferred terms and system organ class using the Medical Dictionary for Regulatory Activities (MedDRA version 21.1 dictionary) terminology.

Immunologic assay data will be stored in a secure location by IDRI. Prior to analysis, the immunologic assay data will be transferred to the Biostatistician (or designee), who will convert it to a SAS dataset.

7 STATISTICAL CONSIDERATIONS

7.1 Determination of Sample Size

This study is a phase 1, randomized, double-blind clinical trial designed to evaluate the safety, tolerability, and immunogenicity of the single-vial and two-vial presentations of ID93 + GLA-SE. As such, the sample size of $n=48$ was determined by what is reasonable for a phase 1 trial and not based on statistical considerations of power, and will allow only preliminary safety and immunogenicity information relevant to progression to larger trials.

7.2 Plan for Statistical Summaries and Analyses

7.2.1 General Considerations

Statistical summaries and analyses of baseline and safety data will be provided for the safety population, defined as all subjects who receive at least one study injection. Summaries and analyses of immune response data will be provided for the per-protocol population. The objectives of the immune response statistical summaries and analyses are to assess the immunogenicity following intramuscular administration of study vaccine among the treatment groups. The goals are:

1. To describe the humoral and cellular response to both vaccine presentations in terms of magnitude and positive response rate
2. To determine if there is a significant difference in the immune response elicited by the two-vial and the single-vial lyophilized vaccine presentation

All individual subject data listings will be provided in appendices to the clinical study report. Data will be summarized and tabulated by treatment group and descriptive statistics will be provided where

appropriate. The immunology analysis will be performed using either SAS version 9.3 or higher or R version 3.5 or higher.

Categorical data will be analyzed using Fisher's exact test using 0.05 level of significance ($\alpha = 0.05$) with Holm-Bonferroni adjustments whenever pairwise comparisons are made between more than two categories.

Continuous data will be compared between two treatment groups using a Two-sample T-test if the normality assumption is met or Wilcoxon Rank-Sum Test, otherwise. Response rates will be compared using a Fisher's Exact test. Significant differences will be detected based on a two-sided test with $p \leq 0.05$ ($\alpha = 0.05$). Comparisons will be accompanied by the point-estimate and 95% CI for each group.

Missing data: The analysis plan assumes that missing data are missing completely at random (MCAR) and analysis will be performed on the available data.

Individual subject data listings will be provided as separate appendices in the CSR. All summaries, statistical analyses, and individual subject data listings will be analyzed by using either SAS version 9.3 or higher or R version 3.5 or higher.

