7.5 Day 56 (± 3) Evaluations and Second Study Injection

Prior to Study Injection:

- Review Inclusion/Exclusion criteria as specified for the second study injection.
- Review adverse events, including SAEs and PIMMCs.

- Review concomitant medications.
- Obtain vital signs (BP, P, RR, oral temperature).
- Perform a targeted physical exam if indicated, based on symptoms.
- Perform urine pregnancy test for females of childbearing potential within 24 hours prior to study injection. Test results must be confirmed as negative prior to study injection.
- Review of acceptable contraceptive methods (female subjects only).
- Counseling on avoidance of pregnancy (for all female subjects of childbearing potential).
- Collect blood prior to study injection for baseline immunologic evaluations for:
 - Serum for IgG ELISA
 - PBMC isolation

Study Injection:

- Administer study injection in the non-dominant deltoid unless there is a reason to inject in the alternate deltoid. Both injections are preferably administered in the same arm.
- Dispense memory aid, measuring tool, and thermometer.

Immediately Following Study Injection:

All subjects will be observed for a minimum of 60 minutes following study injection. After 60 minutes:

- Obtain vital signs (BP, P, RR, oral temperature).
- Examine the injection site and assess any AE/SAEs (including specific solicited systemic reactions: headache, arthralgia, chills, loss of appetite, fever, fatigue, and myalgia), prior to discharge from the clinic.
- Request subject to bring their completed memory aid to the next clinic visit.

All subjects will be asked to record, on a subject memory aid, daily maximum temperatures, symptoms for 7 days, and measure erythema or induration if any beginning with the day of study injection and report them to the clinic staff. Subjects will be asked to bring their completed memory aid to the Day 7 post-injection clinic visit.

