11.2.2 Per Protocol Population

The Per Protocol Population will include all eligible subjects randomized to one of the treatment groups and who received both assigned study injections. Subjects will be classified according to the treatment received. Analysis of immunogenicity endpoints occurring after the second study injection will be performed on this population.

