11.2.4 Immunogenicity Population

The Immunogenicity Population will include all eligible subjects who have received at least one study injection, for whom data concerning post-baseline immunogenicity endpoint measures are available, and major protocol deviations are absent. The post-baseline immunogenicity endpoints may include humoral or cellular responses measured at the protocol-specified time points, or at the time of early termination. Subjects will be classified according to the treatment

received. Immunogenicity analysis will be done using this population or the Per Protocol Population, as appropriate.

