11.5.1 Analysis of Demographics and Disposition

Summaries and descriptive statistics of demographic and baseline characteristics will be provided for the safety population.

The following subject disposition information will be summarized for each treatment group:

- Number of subjects enrolled
- Stratified by enrollment group:
 - Number (%) of subjects receiving one or two study injections
 - Number (%) of subjects who discontinued the study and reasons for discontinuation
 - Number (%) of subjects in the per-protocol population and reasons for those excluded
 - Number (%) of subjects with at least one protocol violation

Protocol violations will be identified by the Medical Monitor (or designee) for the trial.

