16.3	Subject Disposition, Demographic, and Baseline Data: Subject Disposition: Visit Summary
16.4	Subject Disposition, Demographic, and Baseline Data: Subject Disposition: Subjects Who Withdrew from the Study or Were Lost to Follow up
16.5	Subject Disposition, Demographic, and Baseline Data: Subject Demographic Data: Intent to Treat Population
16.6	Subject Disposition, Demographic, and Baseline Data: Subject Disposition: Extent of Exposure: Study Injection Administration
16.7	Safety Data: Adverse Events: Description
16.8	Safety Data: Adverse Events: Intervention
16.9	Safety Data: Adverse Events: Grade 3
16.10	Safety Data: Adverse Events: Deaths, SAE, and PIMMC
16.11	Safety Data: Adverse Events: AE Listings For Subjects Meeting Any Criterion for Suspending Study Injection
16.12	Safety Data: Adverse Events: Local Injection Site Reactions
16.13	Safety Data: Adverse Events: Solicited Systemic Reactions
16.14	Safety Data: Laboratory Studies: Hematology
16.15	Safety Data: Laboratory Studies: Serum Chemistry
16.16	Safety Data: Serum β hCG and Urine Pregnancy Test
16.17	Safety Data: Vital Signs
16.18	Clinical Data: Physical Examinations
16.19	Clinical Data: Medical History
16.20	Clinical Data: Concomitant Medications
16.21	List of Protocol Deviations
16.22	Immunogenicity Data: IgG ELISA: IgG Antibody Response
16.23	Immunogenicity Data: ICS: CD4/CD8 T Cell Response
16.24	Immunogenicity Data: ELISpot: PBMC IFN- γ and IL-10 Response

NARRATIVE TABLES

Table Number	Title
Table 4:	Summary of Demographic Data and Other Baseline Characteristics (Safety Population)
Table 5:	Summary of Study Injection Exposure (Safety Population)
Table 6:	Subjects with Adverse Events by Study Period, Injection Interval, Severity, and Relatedness to Study Injection (Safety Population)
Table 7:	Subjects with Adverse Events Occurring in ≥ 2 Subjects (Safety Population)
Table 8:	Subjects with Local Injection Site Reaction Adverse Events by Post-injection Period (Safety Population)
Table 9:	Subjects with Solicited Systemic Reaction Adverse Events by Post-injection Period (Safety Population)
Table 10:	IgG ELISA: Antibody Response to ID93
Table 11:	PBMC ICS: CD4 T Cell Response to ID93
Table 11:	PBMC ICS: CD8 T Cell Response to ID93
Table 12:	PBMC ELISpot: IFN- γ Response to ID93
Table 13:	PBMC ELISpot: IL-10 Response to ID93

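### SAP 7.2.1 puts every immune-response visit on the two-injection per-protocol population, so a one-dose subject's first-dose results drop out of summaries and tests (low severity)

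*SAP*

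**What the plan says.** The general rule is in SAP 7.2.1: "Summaries and analyses of immune response data will be provided for the per-protocol population". It names no visits. SAP 7.2.3 and the titles of Tables 14.3.1 to 14.3.5 name no population, whereas the adverse-event tables (14.2.1 to 14.2.8) do. So 7.2.1 is the only assignment made in Section 7.

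SAP Section 5 and protocol 11.2.2 define the per-protocol population as eligible randomised subjects who received both assigned injections, and add: "Analysis of immunogenicity endpoints occurring after the second study injection will be performed on this population".

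Both documents also define an Immunogenicity Population: eligible subjects with at least one injection "for whom data concerning post-baseline immunogenicity endpoint measures are available, and major protocol deviations are absent". On the choice between the two they say: "Immunogenicity analysis will be done using this population or the Per Protocol Population, as appropriate".

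SAP 7.2.3 schedules ICS on Days 0, 7, 14, 56, 63, 70, 84 and 224, and IgG and ELISpot on the same days except 7 and 63. Protocol 7.5 lists the Day 56 immunology blood among the steps before the second injection: "Collect blood prior to study injection for baseline immunologic evaluations for".

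**The concern.** Days 7, 14 and 56 measure the response to the first injection only. Whether a subject later receives the second injection has no bearing on whether those results are valid. Under 7.2.1 as written, it decides whether they are analysed.

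That later event is not always unrelated to the response. Protocol 9.6.1 stops further injections after Grade 3 laboratory changes, high fever with constitutional symptoms, or Grade 3 local reactions. Protocol 5.3 withholds the second injection for laboratory values of Grade 2 or worse that have not returned to the protocol-defined normal range. Other causes, such as withdrawn consent, pregnancy or missed visits, need not track the immune response.

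At stake is the first-dose part of a secondary objective, the immunogenicity comparison of the two presentations. Tolerability is also compared between them, so reaction-driven losses could fall unevenly across the arms.

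**Working it through.** **1. Which results are affected.**

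| Visit | Assays (SAP 7.2.3) | Injections received before the sample | Population under 7.2.1 |
|---|---|---|---|
| Day 7 | ICS | 1 | per-protocol |
| Day 14 | IgG, ELISpot, ICS | 1 | per-protocol |
| Day 56 (pre-injection) | IgG, ELISpot, ICS | 1 | per-protocol |
| Day 63 | ICS | 2 | per-protocol |
| Days 70, 84, 224 | IgG, ELISpot, ICS | 2 | per-protocol |

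The first three rows come before the second injection, so the per-protocol sentence in Section 5 does not reach them. Protocol 7.13 follows one-dose subjects for 28 days with scheduled blood samples, so their Day 7 and Day 14 samples should exist. A Day 56 sample often will not, unless the injection is withheld at that visit or the subject agrees to further draws under protocol 5.4.5.

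**2. Inputs.** Arm sizes are 25 (two-vial) and 23 (single-vial), from SAP Table 1. The documents give no number of one-dose subjects, k, and no variance for titres. Assumed, with no basis in the documents: correlation ρ of 0.3 to 0.5 between reactogenicity and log10 titre; SD of log10 titre 0.5 to 0.7; normal distributions; all k losses in one arm and drawn from its most reactive subjects. There is no planned figure to reproduce, because the sample size has no power basis.

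**3. Shift in the Day 14 mean.** Expected shift in SD units = −ρ × (sum of the k largest expected normal order statistics) / (n − k). GMT factor = 10^(shift × SD).

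| n | k | Sum | Shift, ρ = 0.3 | Shift, ρ = 0.5 | GMT factor, mildest to most extreme |
|---|---|---|---|---|---|
| 23 | 1 | 1.929 | −0.0263 | −0.0438 | 0.970 to 0.932 |
| 23 | 2 | 3.411 | −0.0487 | −0.0812 | 0.946 to 0.877 |
| 23 | 3 | 4.625 | −0.0694 | −0.1156 | 0.923 to 0.830 |
| 25 | 1 | 1.965 | −0.0246 | −0.0409 | 0.972 to 0.936 |
| 25 | 2 | 3.490 | −0.0455 | −0.0759 | 0.949 to 0.885 |
| 25 | 3 | 4.752 | −0.0648 | −0.1080 | 0.928 to 0.840 |

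Example: n = 23, k = 2, ρ = 0.5 gives −0.5 × 3.411 / 21 = −0.0812. With SD 0.7, 10^(−0.0568) = 0.877. If one subject is lost from each arm, the shifts differ by only 0.0017 to 0.0029 SD, a factor of 0.998 to 0.995 on the GMT ratio.

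**4. Random error for comparison.** SE of the group difference = √(1/25 + 1/23) = 0.289 SD. With t(46) = 2.013 the 95% half-width is 0.582 SD, a factor of 10^(0.582 × 0.5) = 1.95 to 10^(0.582 × 0.7) = 2.55 each way. The largest shift above is 0.1156/0.582, or 20%, of that half-width.

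**5. Precision.** SE relative to 25 v 23: 24 v 23, 1.010; 25 v 22, 1.012; 23 v 23, 1.021; 25 v 21, 1.025. So one or two losses raise the SE by 1.0% to 2.5%.

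**6. Responder rates, with no correlation assumed.** Leaving out k of n subjects moves an arm's rate by at most k/n: 1/23 = 4.3, 2/23 = 8.7, 1/25 = 4.0 and 2/25 = 8.0 points. For instance, 12/23 (52.2%) becomes 10/21 (47.6%) if two responders go. The 95% half-width for a difference at a 50% rate is 1.96 × √(0.25/25 + 0.25/23) = 28.3 points.

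The titre figures do not apply to Day 7, which has ICS only.

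**The case against.** The best defence is that the documents allow the choice and that it suits the objective. The sentence on using either population as appropriate permits the per-protocol set, and the sentence tying that set to later endpoints does not say it may be used only there. Both secondary objectives concern responses after two injections. A single set also avoids a change in eligible subjects partway along the by-visit line plot. SAP Section 5 says its definitions govern the planned analyses, so 7.2.1 can be read together with it. For ICS, SAP 7.2.3.2.1 bases percentages on all subjects in the treatment group, which blurs the denominator further.

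Most of this stands. A reader might infer that 7.2.1 breaches the protocol, and the documents do not support that: it is a permitted choice that sits badly with the definitions. None of these points, however, gives a reason to make analysis of a first-dose response depend on a later injection.

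Three other strong readings also fail:

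- A reader might set 7.2.1 against its own missing-data sentence, "The analysis plan assumes that missing data are missing completely at random (MCAR) and analysis will be performed on the available data". That sentence concerns how missing values are handled and does not define the population, so there is no contradiction.
- A reader might think the data vanish. Listings 16.22 to 16.24 cover the immunology results, for example "Immunogenicity Data: ICS: CD4/CD8 T Cell Response", and nothing in their titles limits them to the per-protocol set. Protocol 11.5.1 already requires "Number (%) of subjects in the per-protocol population and reasons for those excluded".
- A reader might take the three-subject rule in protocol 9.6.2 as a limit of two one-dose subjects. It is a pause rule for specified related events and caps nothing, hence the k = 3 rows.

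**Conclusion.** The mismatch is real and of low severity. Taken literally, 7.2.1 removes observed first-dose results from summaries and tests through a selection made after dosing, although a population that would keep them is already defined.

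A reader might infer that the first-dose comparison is materially biased. The documents do not show that. The number of one-dose subjects is unknown and may be zero; protocol 2.3.1 reports that no subject in the earlier ID93 + GLA-SE trials it summarises withdrew because of an adverse event. With none, the effect is nil. With balanced losses it is negligible. With one or two reaction-driven losses in one arm, that arm's Day 14 GMT changes by a factor of 0.97 to 0.88, and with three by 0.93 to 0.83, all under the assumed correlation and SD. Each shift is well inside the random error of a trial this size, which tests no formal hypothesis. The point rests on the plan's own definitions and the ease of repair.

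**What to change.** In SAP 7.2.1, assign Days 7, 14 and the pre-injection Day 56 sample to the Immunogenicity Population as already defined, and Days 63, 70, 84 and 224 to the per-protocol population. Apply the same major-deviation rule to both. Only the Immunogenicity Population has that clause now, so a two-dose subject could otherwise be dropped early and kept later. State the population and the N per visit on Tables 14.3.1 to 14.3.5.

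The cost is SAP wording, one population flag and labels on five tables, with no new data. There are two downsides. Denominators will differ before and after the second injection. And the SAP introduction records that the safety analysis has already been performed, so the change should be dated and justified in the SAP, with the all-visit per-protocol result kept as a sensitivity analysis.

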11.5.3 Immunology Analyses

Immunogenicity will be assessed from blood samples obtained on Days 0, 7, 14, 56, 63, 70, 84, and 224. Secondary immunogenicity evaluations will include quantification of T cell cytokine responses from stimulated PBMCs and serum IgG antibody responses to ID93. Exploratory analyses will include measurement of functionality of immune responses through the whole blood mycobacterial growth inhibition assay (MGIA), measurement of humoral responses in mucosal secretions (nasal swabs and tears), quantitation of IgA and IgG secreting B cells and memory B cells, and measurement of the frequencies of peripheral T follicular helper cells, memory B cells, and T cell homing markers.

Immune responses for each treatment group will be evaluated by calculating the response rate and magnitude of response to ID93 at all timepoints for each immunologic endpoint. Comparisons of response rates for IgG and cytokine responses across treatment groups will be made using $n \times m$ Fisher's exact tests. Pairwise comparisons will be done using 2×2 Fisher's exact tests with multiplicity adjustment to control the family-wise error rate (FWER).

The magnitude of IgG and cytokine responses will be compared across treatment groups using ANOVA when the distribution is Gaussian and Kruskal-Wallis when the distribution is non-Gaussian. When ANOVA is used and a difference is observed across the treatment groups, pairwise comparisons will be made using t-tests with adjustment to control the FWER. If Kruskal-Wallis is used, Wilcoxon rank-sum tests will be used.

Percentages of CD4 and CD8 T cells producing selected cytokines will be summarized by time point and compared across and between treatment groups.

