7.2.3 Immune Response

The following are the endpoints of interest:

Primary Analysis Endpoints:

- IgG antibody responses to ID93 by ELISA at Days 0, 14, 56, 70, 84, and 224
 - Mean endpoint titer of ID93-specific antibodies for total IgG on for each treatment group.
 - The proportion of subjects with at least a 4-fold increase in ID93-specific IgG antibody levels on Days 14, 56, 70, 84, and 224 relative to baseline (Day 0).
 - Mean fold change from baseline (Day 0) in IgG antibody responses to ID93.
- T cell responses to ID93 by PBMC ICS on Days 0, 7, 14, 56, 63, 70, 84, and 224
 - The proportion of cells expressing any two of IFN- γ , TNF, IL-2, IL-4, IL-21, or CD154 in response to ID93.
 - The polyfunctionality based on expression of IFN- γ , TNF, IL-2, IL-4, IL-21, or CD154.
- T cell responses to ID93 by ELISpot on Days 0, 14, 56, 70, 84 and 224
 - The number of IFN- γ cytokine-secreting cells in PBMC samples in response to the ID93 antigen relative to baseline (Day 0) at Days 14, 56, 70, 84, and 224, as assayed by ELISpot.

Secondary and Exploratory Analysis Endpoints:

- IgG subclass antibody responses to ID93 by ELISA at Days 0, 14, 56, 70, 84, and 224

- The proportion of subjects with at least a 4-fold increase in ID93-specific IgG1, IgG2, IgG3, and IgG4 antibody levels on Days 14, 56, 70, 84, and 224 relative to baseline (Day 0).
- Mean endpoint titer of ID93-specific antibodies for IgG1, IgG2, IgG3, and IgG4 on for each treatment group.

Immune responses for each treatment group will be evaluated by calculating the response rate and magnitude of response to ID93 at all timepoints for each immunologic endpoint. Comparisons of response rates for IgG and cytokine responses between treatment groups will be made using Fisher's exact tests.

The magnitude of IgG and cytokine responses will be compared between treatment groups using a Two-sample T-test if normality assumption is met or Wilcoxon Rank-Sum Test, otherwise.

Percentages of CD4+ cells producing selected immune markers will be summarized by time point and compared between treatment groups.

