7.2.3.1 IgG Antibody Response to ID93

IgG antibody responses (Total IgG, IgG1, IgG2, IgG3, and IgG4) to the ID93 antigen will be measured by ELISA using serum collected from a given subject. Specimens from all time points for a given subject will be analyzed on a single ELISA plate. The plate will contain standards and controls that will be used to determine plate validity based on criteria established during assay validation.

At each timepoint, the IgG mean endpoint titer (**Total IgG MEPT**) value calculated from duplicates or triplicates will be reported.

At each post-injection timepoint, the following **Post:Pre Ratio** will be calculated:

$$\text{Post:Pre Ratio} = \frac{\text{MEPT (Post-Injection Timepoint)}}{\text{MEPT (Baseline Timepoint)}}$$

A subject will be considered an antibody positive **Responder** at a given timepoint if:

- a) System suitability criteria for a given ELISA are met; and
- b) The Post:Pre Ratio at that timepoint is ≥ 4 .

The following **listing** is planned:

- Humoral Response: IgG ELISA: IgG Antibody Response

- This listing will be organized by treatment group and will include: Subject ID, Visit Day, Collection Date, IgG MEPT, Post:Pre Ratio, Responder (Yes/No)

The following **tables** are planned:

- Humoral Response: IgG ELISA: IgG Antibody Response
 - This is a tabulation by Visit Day of the Total IgG MEPT, Post:Pre Ratio, and Responder status of each treatment group. The table will include descriptive statistics and a statistical comparison of each parameter between the two treatment groups.
- A Narrative Table will be prepared and will include
 - Percent responder status at each time point with p-value of the statistical comparison of the treatment groups

The following **figure** is planned:

- Humoral Response: IgG ELISA: IgG Antibody Response
 - IgG MEPT (log10) by study visit and treatment group.
 - Repeated for each IgG subclass
 - This will be a line plot with error bars representing +/- 95% CI.

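### With two arms, the SAP's Holm-Bonferroni clause adjusts none of the roughly 63 between-group immune tests, and no key comparison is named

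*SAP*

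**What the plan says.** SAP 7.2.1 sets two goals for the immune analysis. The second is "To determine if there is a significant difference in the immune response elicited by the two-vial and the single-vial lyophilized vaccine presentation". The testing rules follow in the same section:

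- Categorical data: "Categorical data will be analyzed using Fisher's exact test using 0.05 level of significance", and then "with Holm-Bonferroni adjustments whenever pairwise comparisons are made between more than two categories".
- Continuous data: two-sample t-test or Wilcoxon rank-sum test, with no adjustment stated.
- Significance: "Significant differences will be detected based on a two-sided test with" p ≤ 0.05. A point estimate and 95% CI are promised for each group, but not for the difference between groups.

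SAP section 5 defines treatment group as "One of the two treatment assignments".

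Protocol 11.5.3 foresees overall tests across treatment groups, followed by pairwise 2 × 2 Fisher tests "with multiplicity adjustment to control the family-wise error rate (FWER" and, after ANOVA, pairwise t-tests with similar adjustment. SAP 7.2.3 replaces this with plain two-group tests.

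SAP 7.2.3 lists several endpoints from three assays as primary for the immune analysis, without a hierarchy or a lead visit. Protocol 11.3 says that the study was not set up to test a formal hypothesis, and both documents describe the information as preliminary.

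**The concern.** A reader who sees a Holm sentence in the SAP and FWER wording in the protocol may assume that multiplicity in the arm comparison has been handled. In both documents the wording concerns pairwise comparisons among several groups or categories, and this trial has two groups. The multiplicity that does exist runs across assays, cell types, parameters and visits, and no rule addresses it.

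This matters because goal 2 and the p ≤ 0.05 rule together invite a finding of difference, while the protocol disclaims formal testing. Protocol 2.2 calls this a bridging study meant to let the single-vial product move forward. A chance difference at one visit in one assay could be given weight in that decision, and the plan gives no prior ranking against which to judge it.

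**Working it through.** **Plan's own figure.** The documents state neither a number of comparisons nor a family-wise error rate. Their only design calculation is Protocol Table 2, the chance of seeing at least one event, 1 − (1 − p)^n. All 12 cells reproduce; for example, 1 − 0.95^20 = 64.2% against the stated 64%. It concerns safety events and does not bear on this point.

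**Step 1: does the clause act?** With k groups there are k(k − 1)/2 pairwise contrasts. For k = 2 that is 1, and Holm gives 0.05/1 = 0.05, which is no adjustment. For k = 3 it would be 3, with a first step of 0.05/3 = 0.0167. Reading categories as outcome levels does not change this. Every planned between-group Fisher test (SAP 7.2.2.2, 7.2.2.3, 7.2.3) compares two groups on a yes/no outcome. Severity grades have three levels but are only summarised.

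**Step 2: count of post-baseline between-group immune tests.** The count is built from the planned tables.

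| Assay | Source | Parameters × visits | Tests |
|---|---|---|---|
| Total IgG | SAP 7.2.3.1: "The table will include descriptive statistics and a statistical comparison of each parameter between the two treatment groups"; visits from 7.2.3: "IgG antibody responses to ID93 by ELISA at Days 0, 14, 56, 70, 84, and 224" | titre, ratio, responder (3) × 5 | 15 |
| ICS (at least two markers) | SAP 7.2.3.2.1 | CD4/CD8 (2) × median/responder rate (2) × 7 | 28 |
| ELISpot | SAP 7.2.3.2.2 | IFN-γ/IL-10 (2) × median/responder rate (2) × 5 | 20 |
| Total | | | **63** |

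The expected number of false positives is 0.05 × m. Under independence, P(at least one) = 1 − 0.95^m.

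| Family counted | m | Expected | P(at least one), independent |
|---|---|---|---|
| Without IL-10 | 53 | 2.65 | 93.4% |
| Without IL-10 responder rates | 58 | 2.90 | 94.9% |
| As above | 63 | 3.15 | 96.0% |
| Adding Day 0 where a value exists | 72 | 3.60 | 97.5% |
| 63 plus subclass titre and responder rate (4 × 5 × 2 = 40) | 103 | 5.15 | 99.5% |

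The selected ICS marker combinations would add a number that the SAP does not state.

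**Step 3: correlation.** The documents give no correlations, so these are assumptions. Simulating 63 equicorrelated normal statistics (200,000 draws), each tested at two-sided 0.05, gives:

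| Assumed correlation | 0 | 0.3 | 0.5 | 0.7 | 0.9 |
|---|---|---|---|---|---|
| P(at least one) | 96% | 86% | 68% | 44% | 20% |

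The expected count stays at 3.15 throughout.

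**Step 4: Fisher's conservatism.** Of the 63 tests, 34 concern magnitude (10 + 14 + 10) and 29 are responder tests (5 + 14 + 10). With the SAP Table 1 sizes of 25 and 23, the true size of Fisher's test at nominal 0.05 runs from 0.008 to 0.040 for assumed common responder rates between 0.10 and 0.95. The expected number of false positives is then:

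- lowest: 34 × 0.05 + 29 × 0.0079 = 1.70 + 0.23 = 1.93
- highest: 34 × 0.05 + 29 × 0.0398 = 1.70 + 1.16 = 2.86

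Under independence the chance of at least one is then 86% to 95%.

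**The case against.** The strongest reply is that the plan breaks no promise. Protocol 11.5.3 ties FWER control to pairwise comparisons between treatment groups, and SAP 7.2.1 makes Holm conditional. With one contrast, that family has one member and its error rate is 0.05. This stands. A reader might infer that the documents claim control across endpoints and visits and fail to deliver it, but neither makes that claim. The wording is empty, not false.

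Four further points qualify the concern:

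- A reader might infer that no multiplicity adjustment can operate anywhere in the plan. That goes too far. SAP 7.2.3.3 has a separate, conditional adjustment of the antigen-versus-background tests that classify each subject as an ELISpot responder. It may well operate, but it does not touch comparisons between arms.
- It is tempting to say that a false positive is nearly certain. That needs independence. The tests reuse the same subjects over visits, and the three IgG parameters come from one titre, so positive correlation is likely.
- A reader might fear selective reporting. The SAP plans p-values by visit and lists its tables in advance, so only the emphasis is open.
- The trial is unpowered and preliminary, and a false positive here counts against the new presentation. Missing a real difference may be the greater hazard in a bridging study, and heavy adjustment would worsen it. This is a sound reason not to apply Holm to all 63 tests. It does not justify keeping an inert sentence beside a goal framed in terms of significance.

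**Conclusion.** The point holds for comparisons between arms. The Holm clause adjusts none of them, the protocol's FWER wording is equally empty with two groups, and about 63 tests at 0.05 serve goal 2 with no key comparison named. That goal and its significance rule sit in conflict with the protocol's statement that no formal hypothesis is tested.

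If the presentations are truly identical, up to 3.15 false positives are expected, or about 1.9 to 2.9 after allowing for Fisher's test. The chance of at least one lies between 96% (independence) and about 20% (assumed equicorrelation of 0.9). Even the last figure is four times the nominal 5%.

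These results assume that all 48 subjects contribute, although the immune analysis uses the per-protocol population, and that the t-test and Wilcoxon hold their nominal level. The count of 63 is derived from planned outputs. The 103 figure is less firm, because the SAP's comparison table names total IgG and only the figure is explicitly repeated for subclasses. Given the trial's preliminary status, this is a cheap improvement and not a fatal flaw.

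**What to change.** Replace the inoperative Holm sentence in SAP 7.2.1 with one of two statements, and align goal 2 with it:

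1. All between-group immune p-values are descriptive and no significance claims will be made. This fits Protocol 11.3 best.
2. One key comparison is named per assay, with endpoint and visit chosen by the sponsor. Holm is applied across those few (with three, a first step of 0.05/3 = 0.0167), and everything else is descriptive. The SAP introduction says that the safety analysis was already done when this immunology amendment was written, so the SAP should also state whether any immunology data had been seen when the choice was made.

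Under either option, report between-group differences or ratios with 95% CIs, in addition to the per-group intervals. State that a non-significant p-value is not evidence that the presentations are similar.

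Applying Holm to all 63 tests is not advised: its first step would be 0.05/63 = 0.00079, which makes a real difference very hard to declare.

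The cost is a change to SAP wording and some added table columns, with no new data. The downside is that fewer endpoints can be called significant.
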